Appendix B: Rivaroxaban vs Warfarin

COPD; n (%)	4,309 (16.8%)	2,430 (16.3%)	0.01	4,571 (14.2%)	2,352 (13.3%)	0.03	18,074 (19.6%)	8,952 (22.0%)	-0.06	26954 (17.9%)	13734 (18.7%)	-0.02
Asthma; n (%)	1,542 (6.0%)	1,081 (7.3%)	-0.05	1,625 (5.0%)	1,171 (6.6%)	-0.07	6,360 (6.9%)	3,495 (8.6%)	-0.06	9527 (6.3%)	5747 (7.8%)	-0.06
Obstructive sleep apnea; n (%)	2,457 (9.6%)	1,923 (12.9%)	-0.10	2,936 (9.1%)	2,260 (12.7%)	-0.12	7,564 (8.2%)	4,077 (10.0%)	-0.06	12957 (8.6%)	8260 (11.3%)	-0.09
Pneumonia; n (%)	1,531 (6.0%)	901 (6.1%)	0.00	1,914 (5.9%)	1,034 (5.8%)	0.00	8,764 (9.5%)	4,313 (10.6%)	-0.04	12209 (8.1%)	6248 (8.5%)	-0.01
Imaging; n (%)	36 (0.1%)	27 (0.2%)	-0.03	44 (0.1%)	15 (0.1%)	0.00	3,729 (4.0%)	1,328 (3.3%)	0.04	3809 (2.5%)	1370 (1.9%)	0.04
Other Medications												
Use of ACE inhibitors; n (%)	9,773 (38.0%)	5,230 (35.2%)	0.06	11,540 (35.7%)	6,215 (35.0%)	0.01	35,261 (38.2%)	15,477 (38.1%)	0.00	56574 (37.6%)	26922 (36.7%)	0.02
Use of ARBs; n (%)	5,359 (20.9%)	3,889 (26.2%)	-0.13	7,683 (23.8%)	4,892 (27.6%)	-0.09	20,854 (22.6%)	10,920 (26.9%)	-0.10	33896 (22.5%)	19701 (26.9%)	-0.10
Use of Loop Diuretics - United; n (%)	7,760 (30.2%)	3,674 (24.7%)	0.12	10,702 (33.1%)	3,963 (22.3%)	0.24	40,069 (43.4%)	15,255 (37.5%)	0.12	58531 (38.9%)	22892 (31.2%)	0.16
Use of other diuretics- United; n (%)	1,535 (6.0%)	731 (4.9%)	0.05	2,341 (7.2%)	878 (4.9%)	0.10	7,877 (8.5%)	2,806 (6.9%)	0.06	11753 (7.8%)	4415 (6.0%)	0.07
Use of nitrates-United; n (%)	2,055 (8.0%)	1,038 (7.0%)	0.04	3,094 (9.6%)	1,354 (7.6%)	0.07	10,921 (11.8%)	4,642 (11.4%)	0.01	16070 (10.7%)	7034 (9.6%)	0.04
Use of other hypertension drugs; n (%)	2,028 (7.9%)	1,125 (7.6%)	0.01	2,574 (8.0%)	1,303 (7.3%)	0.03	7,958 (8.6%)	3,455 (8.5%)	0.00	12560 (8.4%)	5883 (8.0%)	0.01
Use of digoxin- United; n (%)	4,005 (15.6%)	1,311 (8.8%)	0.21	6,378 (19.7%)	1,975 (11.1%)	0.24	17,796 (19.3%)	5,477 (13.5%)	0.16	28179 (18.7%)	8763 (12.0%)	0.19
Use of Anti-arrhythmics; n (%)	2,453 (9.5%)	2,071 (13.9%)	-0.14	3,881 (12.0%)	2,847 (16.0%)	-0.12	10,257 (11.1%)	6,110 (15.0%)	-0.12	16591 (11.0%)	11028 (15.1%)	-0.12
Use of COPD/asthma meds- United; n (%)	4,206 (16.4%)	2,858 (19.2%)	-0.07	5,916 (18.3%)	3,513 (19.8%)	-0.04	18,597 (20.1%)	9,406 (23.1%)	-0.07	28719 (19.1%)	15777 (21.5%)	-0.06
Use of statins; n (%)	15,187 (59.1%)	9,008 (60.6%)	-0.03	19,252 (59.6%)	10,616 (59.8%)	0.00	56,100 (60.7%)	25,111 (61.8%)	-0.02	90539 (60.2%)	44735 (61.1%)	-0.02
Use of other lipid-lowering drugs; n (%)	1,698 (6.6%)	959 (6.4%)	0.01	3,164 (9.8%)	1,658 (9.3%)	0.02	6,803 (7.4%)	2,989 (7.4%)	0.00	11665 (7.8%)	5606 (7.7%)	0.00
Use of antiplatelet agents; n (%)	2,667 (10.4%)	2,234 (15.0%)	-0.14	4,187 (13.0%)	2,985 (16.8%)	-0.11	12,151 (13.2%)	7,088 (17.4%)	-0.12	19005 (12.6%)	12307 (16.8%)	-0.12
Use of heparin and other low-molecular weight heparins; n (%)	1,027 (4.0%)	48 (0.3%)	0.26	13 (0.0%)	2 (0.0%)	#DIV/0!	5,378 (5.8%)	271 (0.7%)	0.29	6418 (4.3%)	321 (0.4%)	0.26
Use of NSAIDs; n (%)	2,211 (8.6%)	1,854 (12.5%)	-0.13	2,679 (8.3%)	2,192 (12.4%)	-0.13	8,445 (9.1%)	5,496 (13.5%)	-0.14	13335 (8.9%)	9542 (13.0%)	-0.13
Use of oral corticosteroids; n (%)	4,525 (17.6%)	3,114 (20.9%)	-0.08	5,871 (18.2%)	3,585 (20.2%)	-0.05	20,413 (22.1%)	10,417 (25.6%)	-0.08	30809 (20.5%)	17116 (23.4%)	-0.07
Use of bisphosphonate (United); n (%)	1,032 (4.0%)	504 (3.4%)	0.03	1,328 (4.1%)	488 (2.7%)	0.08	3,634 (3.9%)	1,530 (3.8%)	0.01	5994 (4.0%)	2522 (3.4%)	0.03
Use of opioids- United; n (%)	5,799 (22.6%)	3,261 (21.9%)	0.02	7,739 (24.0%)	4,176 (23.5%)	0.01	25,851 (28.0%)	11,903 (29.3%)	-0.03	39389 (26.2%)	19340 (26.4%)	0.00
Use of antidepressants; n (%)	4,895 (19.0%)	3,065 (20.6%)	-0.04	6,023 (18.6%)	3,323 (18.7%)	0.00	22,801 (24.7%)	10,978 (27.0%)	-0.05	33719 (22.4%)	17366 (23.7%)	-0.03
Use of antipsychotics; n (%)	375 (1.5%)	238 (1.6%)	-0.01	504 (1.6%)	250 (1.4%)	0.02	2,418 (2.6%)	1,335 (3.3%)	-0.04	3297 (2.2%)	1823 (2.5%)	-0.02
Use of anticonvulsants; n (%)	2,989 (11.6%)	1,777 (12.0%)	-0.01	3,445 (10.7%)	1,742 (9.8%)	0.03	13,599 (14.7%)	6,653 (16.4%)	-0.05	20033 (13.3%)	10172 (13.9%)	-0.02
Use of lithium- United; n (%)	13 (0.1%)	12 (0.1%)	0.00	23 (0.1%)	18 (0.1%)	0.00	29 (0.0%)	30 (0.1%)	-0.04	65 (0.0%)	60 (0.1%)	-0.04
Use of Benzos- United; n (%)	2,295 (8.9%)	1,810 (12.2%)	-0.11	4,007 (12.4%)	2,389 (13.5%)	-0.03	10,742 (11.6%)	6,233 (15.3%)	-0.11	17044 (11.3%)	10432 (14.2%)	-0.09
Use of anxiolytics/hypnotics- United; n (%)	1,231 (4.8%)	865 (5.8%)	-0.04	2,019 (6.3%)	1,221 (6.9%)	-0.02	5,918 (6.4%)	3,005 (7.4%)	-0.04	9168 (6.1%)	5091 (6.9%)	-0.03
Use of dementia meds- United; n (%)	988 (3.8%)	571 (3.8%)	0.00	1,481 (4.6%)	546 (3.1%)	0.08	5,159 (5.6%)	2,315 (5.7%)	0.00	7628 (5.1%)	3432 (4.7%)	0.02
Use of antiparkinsonian meds- United; n (%)	695 (2.7%)	399 (2.7%)	0.00	923 (2.9%)	441 (2.5%)	0.02	3,529 (3.8%)	1,659 (4.1%)	-0.02	5147 (3.4%)	2499 (3.4%)	0.00
Any use of pramlintide; n (%)	3 (0.0%)	3 (0.0%)	#DIV/0!	4 (0.0%)	2 (0.0%)	#DIV/0!	**	**	#VALUE!	#VALUE!	#VALUE!	#VALUE!
Any use of 1st generation sulfonylureas; n (%)	1 (0.0%)	0 (0.0%)	#DIV/0!	14 (0.0%)	1 (0.0%)	#DIV/0!	**	**	#VALUE!	#VALUE!	#VALUE!	0.00
Entresto (sacubitril/valsartan); n (%)	64 (0.2%)	67 (0.5%)	-0.05	18 (0.1%)	29 (0.2%)	-0.03	87 (0.1%)	88 (0.2%)	-0.03	169 (0.1%)	184 (0.3%)	0.00
Labs												
Lab values- HbA1c (%) v3; n (%)	3,444 (13.4%)	2,695 (18.1%)	-0.13	456 (1.4%)	242 (1.4%)	0.00	N/A	N/A	#VALUE!	3,900 (6.7%)	2,937 (9.0%)	-0.09
Lab values- HbA1c (%) (within 3 months) v3; n (%)	2,217 (8.6%)	1,747 (11.7%)	-0.10	321 (1.0%)	170 (1.0%)	0.00	N/A	N/A	#VALUE!	2,538 (4.4%)	1,917 (5.9%)	-0.07
Lab values- HbA1c (%) (within 6 months) v3; n (%)	3,444 (13.4%)	2,695 (18.1%)	-0.13	456 (1.4%)	242 (1.4%)	0.00	N/A	N/A	#VALUE!	3,900 (6.7%)	2,937 (9.0%)	-0.09
Lab values- BNP; n (%)	401 (1.6%)	281 (1.9%)	-0.02	35 (0.1%)	28 (0.2%)	-0.03	N/A	N/A	#VALUE!	436 (0.8%)	309 (0.9%)	-0.01
Lab values- BNP (within 3 months); n (%)	281 (1.1%)	224 (1.5%)	-0.04	28 (0.1%)	18 (0.1%)	0.00	N/A	N/A	#VALUE!	309 (0.5%)	242 (0.7%)	-0.03
Lab values- BNP (within 6 months); n (%)	401 (1.6%)	281 (1.9%)	-0.02	35 (0.1%)	28 (0.2%)	-0.03	N/A	N/A	#VALUE!	436 (0.8%)	309 (0.9%)	-0.01
Lab values- BUN (mg/dl); n (%)	6,014 (23.4%)	4,675 (31.4%)	-0.18	409 (1.3%)	390 (2.2%)	-0.07	N/A	N/A	#VALUE!	6,423 (11.1%)	5,065 (15.5%)	-0.13
Lab values- BUN (mg/dl) (within 3 months); n (%)	4,107 (16.0%)	3,320 (22.3%)	-0.16	282 (0.9%)	290 (1.6%)	-0.06	N/A	N/A	#VALUE!	4,389 (7.6%)	3,610 (11.1%)	-0.12
Lab values- BUN (mg/dl) (within 6 months); n (%)	6,014 (23.4%)	4,675 (31.4%)	-0.18	409 (1.3%)	390 (2.2%)	-0.07	N/A	N/A	#VALUE!	6,423 (11.1%)	5,065 (15.5%)	-0.13
Lab values- Creatinine (mg/dl) v2; n (%)	6,112 (23.8%)	4,840 (32.6%)	-0.20	423 (1.3%)	412 (2.3%)	-0.08	N/A	N/A	#VALUE!	6,535 (11.3%)	5,252 (16.1%)	-0.14
Lab values- Creatinine (mg/dl) (within 3 months) v2; n (%)	4,168 (16.2%)	3,454 (23.2%)	-0.18	293 (0.9%)	308 (1.7%)	-0.07	N/A	N/A	#VALUE!	4,461 (7.7%)	3,762 (11.5%)	-0.13
Lab values- Creatinine (mg/dl) (within 6 months) v2; n (%)	6,112 (23.8%)	4,840 (32.6%)	-0.20	423 (1.3%)	412 (2.3%)	-0.08	N/A	N/A	#VALUE!	6,535 (11.3%)	5,252 (16.1%)	-0.14
Lab values- HDL level (mg/dl); n (%)	4,306 (16.8%)	3,409 (22.9%)	-0.15	373 (1.2%)	270 (1.5%)	-0.03	N/A	N/A	#VALUE!	4,679 (8.1%)	3,679 (11.3%)	-0.11
Lab values- HDL level (mg/dl) (within 3 months); n (%)	2,689 (10.5%)	2,126 (14.3%)	-0.12	251 (0.8%)	181 (1.0%)	-0.02	N/A	N/A	#VALUE!	2,940 (5.1%)	2,307 (7.1%)	-0.08
Lab values- HDL level (mg/dl) (within 6 months); n (%)	4,306 (16.8%)	3,409 (22.9%)	-0.15	373 (1.2%)	270 (1.5%)	-0.03	N/A	N/A	#VALUE!	4,679 (8.1%)	3,679 (11.3%)	-0.11
Lab values- LDL level (mg/dl) v2; n (%)	4,523 (17.6%)	3,538 (23.8%)	-0.15	452 (1.4%)	279 (1.6%)	-0.02	N/A	N/A	#VALUE!	4,975 (8.6%)	3,817 (11.7%)	-0.10
Lab values- LDL level (mg/dl) (within 3 months) v2; n (%)	2,835 (11.0%)	2,212 (14.9%)	-0.12	296 (0.9%)	185 (1.0%)	-0.01	N/A	N/A	#VALUE!	3,131 (5.4%)	2,397 (7.3%)	-0.08
Lab values- LDL level (mg/dl) (within 6 months) v2; n (%)	4,523 (17.6%)	3,538 (23.8%)	-0.15	452 (1.4%)	279 (1.6%)	-0.02	N/A	N/A	#VALUE!	4,975 (8.6%)	3,817 (11.7%)	-0.10
Lab values- NT-proBNP; n (%)	48 (0.2%)	41 (0.3%)	-0.02	5 (0.0%)	4 (0.0%)	#DIV/0!	N/A	N/A	#VALUE!	53 (0.1%)	45 (0.1%)	0.00
Lab values- NT-proBNP (within 3 months); n (%)	37 (0.1%)	34 (0.2%)	-0.03	2 (0.0%)	3 (0.0%)	#DIV/0!	N/A	N/A	#VALUE!	39 (0.1%)	37 (0.1%)	-
Lab values- NT-proBNP (within 6 months); n (%)	48 (0.2%)	41 (0.3%)	-0.02	5 (0.0%)	4 (0.0%)	#DIV/0!	N/A	N/A	#VALUE!	53 (0.1%)	45 (0.1%)	-
Lab values- Total cholesterol (mg/dl) v2; n (%)	4,382 (17.0%)	3,446 (23.2%)	-0.16	372 (1.2%)	269 (1.5%)	-0.03	N/A	N/A	#VALUE!	4,754 (8.2%)	3,715 (11.4%)	-0.11
Lab values- Total cholesterol (mg/dl) (within 3 months) v2; n (%)	2,738 (10.7%)	2,151 (14.5%)	-0.11	246 (0.8%)	180 (1.0%)	-0.02	N/A	N/A	#VALUE!	2,984 (5.1%)	2,331 (7.1%)	-0.08

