Appendix A

3c	Indication for anticoagulant therapy for a condition other than atrial fibrillation (e.g., VTE)	
Measured 180 days prior to and including day of drug initiation in any diagnosis position and inpatient or outpatient care setting:
 
1) Pulmonary embolism (PE): ICD-9 diagnosis: 415.xx ICD-10 diagnosis: I26.xx,
 
2) Deep vein thrombosis (DVT): ICD-9 diagnosis: 451.xx, 453.xx ICD-10 diagnosis: I26.xx, I80.xx, I81.xx, I82.xx, I26.xx
	
3d	
Treatment with:
 
 - Aspirin >100 mg daily - Aspirin in combination with thienopyridines within 5 days before randomization - Intravenous antiplatelets within 5 days before randomization - Fibrinolitics within 10 days before randomization - Note: Aspirin ≤100 mg monotherapy is allowed and thienopyridine monotherapy is allowed. 	
Measured 180 days prior to and including day of drug initiation: Aspirin dose >100mg: (Only prescription use is captured.)
 
Measured 10 days prior to and including day of drug initiation: Fibrinolytic agents: Alteplase, reteplase, tenecteplase, streptokinase, urokinase
 
Measured 5 days prior to and including day of drug initiation: Aspirin (any dose) + thienopyridines (clopidogrel or prasugrel or ticlopidine):
 
Measured 5 days prior to and including day of drug initiation: Cangrelor:
	
3e	Anticipated need for chronic treatment with a non-steroidal anti-inflammatory drug		
3f	Systemic treatment with a strong inhibitor of cytochrome P450 3A4, such as ketoconazole or protease inhibitors, within 4 days before randomization, or planned treatment during the time period of the study	
Measured 4 days prior to and including day of drug initiation as a dispensing of the following:
 
CYP inhibitors (selected): ketoconazole, metronidazole, amiodarone, cimetidine, omeprazole, fluoxetine, indinavir, ritonavir
	
3g	Treatment with a strong inducer of cytochrome P450 3A4, such as rifampin/rifampicin, within 4 days before randomization, or planned treatment during the time period of the study	
CYP inducers (selected): carbamazepine, phenytoin, rifampin/rifampicin, phenobarbital
	

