Bone mineral density; n (%)	805 (3.1%)	532 (3.6%)	-0.03	452 (1.4%)	276 (1.6%)	-0.02	3,027 (3.3%)	1,480 (3.6%)	-0.02	4284 (2.8%)	2288 (3.1%)	-0.02
Use of Sympathomimetic agents; n (%)	51 (0.2%)	60 (0.4%)	-0.04	104 (0.3%)	95 (0.5%)	-0.03	205 (0.2%)	119 (0.3%)	-0.02	360 (0.2%)	274 (0.4%)	-0.04
Use of CNS stimulants; n (%)	48 (0.2%)	45 (0.3%)	-0.02	111 (0.3%)	93 (0.5%)	-0.03	163 (0.2%)	109 (0.3%)	-0.02	322 (0.2%)	247 (0.3%)	-0.02
Use of estrogens, progestins, androgens; n (%)	559 (2.2%)	471 (3.2%)	-0.06	1,035 (3.2%)	806 (4.5%)	-0.07	2,155 (2.3%)	1,280 (3.1%)	-0.05	3749 (2.5%)	2557 (3.5%)	-0.06
Use of Angiogenesis inhibitors; n (%)	6 (0.0%)	4 (0.0%)	#DIV/0!	10 (0.0%)	5 (0.0%)	#DIV/0!	24 (0.0%)	14 (0.0%)	#DIV/0!	40 (0.0%)	23 (0.0%)	#DIV/0!
Use of Oral Immunosuppressants; n (%)	5 (0.0%)	1 (0.0%)	#DIV/0!	21 (0.1%)	7 (0.0%)	0.04	24 (0.0%)	**	#VALUE!	50 (0.0%)	#VALUE!	#VALUE!
Use of fondaparinux or Bivalirudin; n (%)	13 (0.1%)	1 (0.0%)	0.04	14 (0.0%)	3 (0.0%)	#DIV/0!	43 (0.0%)	11 (0.0%)	#DIV/0!	70 (0.0%)	15 (0.0%)	#DIV/0!
Use of other direct thrombin inhibitors (lepirudin, desirudin, argatroban); n (%)	0 (0.0%)	0 (0.0%)	#DIV/0!	0 (0.0%)	0 (0.0%)	#DIV/0!	0 (0.0%)	0 (0.0%)	#DIV/0!	0 (0.0%)	0 (0.0%)	#DIV/0!
Use of Ticagrelor ON CED; n (%)	18 (0.1%)	40 (0.3%)	-0.04	29 (0.1%)	29 (0.2%)	-0.03	30 (0.0%)	19 (0.0%)	#DIV/0!	77 (0.1%)	88 (0.1%)	0.00
Use of Ticagrelor; n (%)	33 (0.1%)	68 (0.5%)	-0.07	38 (0.1%)	48 (0.3%)	-0.04	208 (0.2%)	143 (0.4%)	-0.04	279 (0.2%)	259 (0.4%)	-0.04
Number of D-dimer tests												
...mean (sd)	0.02 (0.17)	0.03 (0.21)	-0.05	0.01 (0.13)	0.03 (0.20)	-0.12	0.03 (0.19)	0.05 (0.23)	-0.09	0.02 (0.18)	0.04 (0.22)	0.00
...median [IQR]	0.00 [0.00, 0.00]	0.00 [0.00, 0.00]	0.00	0.00 [0.00, 0.00]	0.00 [0.00, 0.00]	0.00	0.00 [0.00, 0.00]	0.00 [0.00, 0.00]	0.00	0.00 (0.19)	0.00 (0.25)	0.00
Number of CRP, high-sensitivity CRP tests												
...mean (sd)	0.05 (0.33)	0.07 (0.36)	-0.06	0.03 (0.23)	0.04 (0.27)	-0.04	0.08 (0.42)	0.10 (0.47)	-0.04	0.06 (0.37)	0.08 (0.41)	0.00
...median [IQR]	0.00 [0.00, 0.00]	0.00 [0.00, 0.00]	0.00	0.00 [0.00, 0.00]	0.00 [0.00, 0.00]	0.00	0.00 [0.00, 0.00]	0.00 [0.00, 0.00]	0.00	0.00 (0.40)	0.00 (0.44)	0.00
Number of PT or aPTT tests												
...mean (sd)	2.81 (4.00)	0.46 (1.30)	0.79	2.00 (3.43)	0.37 (1.15)	0.64	3.70 (4.84)	0.42 (1.13)	0.93	3.18 (4.43)	0.42 (1.17)	0.01

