Treating prescriber - Other; n (%)	21,098 (82.1%)	12,821 (86.2%)	-0.11	24,503 (75.9%)	14,433 (81.3%)	-0.13	77,468 (83.8%)	36,185 (89.0%)	-0.15	123069 (81.8%)	63439 (86.6%)	-0.13
Alpha blockers; n (%)	3,114 (12.1%)	1,816 (12.2%)	0.00	4,170 (12.9%)	2,035 (11.5%)	0.04	11,524 (12.5%)	5,009 (12.3%)	0.01	18808 (12.5%)	8860 (12.1%)	0.01
CHADS2 score, 180 days, V												
...mean (sd)	2.22 (1.17)	1.98 (1.19)	0.20	2.23 (1.18)	2.05 (1.20)	0.15	3.80 (1.61)	3.62 (1.65)	0.11	3.19 (1.46)	2.91 (1.47)	0.00
...median [IQR]	2.00 [1.00, 3.00]	2.00 [1.00, 3.00]	0.00	2.00 [1.00, 3.00]	2.00 [1.00, 3.00]	0.00	4.00 [3.00, 5.00]	3.00 [2.00, 5.00]	0.61	1.63 (1.64)	1.62 (1.61)	0.00
Use of Prasugrel; n (%)	43 (0.2%)	58 (0.4%)	-0.04	69 (0.2%)	88 (0.5%)	-0.05	**	**	#VALUE!	#VALUE!	#VALUE!	#VALUE!
Use of Loop Diuretics+other diuretics+other hypertension drugs; n (%)	9,459 (36.8%)	4,643 (31.2%)	0.12	12,825 (39.7%)	5,131 (28.9%)	0.23	45,778 (49.5%)	17,784 (43.7%)	0.12	68062 (45.3%)	27558 (37.6%)	0.16
Commercial vs Medicare Advantage- Business Type												
Code - CORRECT ONE - OPTUM												
...Commercial; n (%)	3,292 (12.8%)	3244 (21.8%)	-0.24	27,877 (86.3%)	13,057 (73.6%)	0.32	-	-	#VALUE!	31,169 (53.7%)	16,301 (50.0%)	0.07
...Medicare Advantage; n (%)	22,409 (87.2%)	11625 (78.2%)	0.24	4,418 (13.7%)	4,691 (26.4%)	-0.32	-	-	#VALUE!	26,827 (46.3%)	16,316 (50.0%)	-0.07
Commercial vs Medicare Advantage- Business Type												
Code												
...COM = COMMERCIAL; n (%)	3,292 (12.8%)	3,244 (21.8%)	-0.24	-	-	-	-	-	#VALUE!	3,292 (12.8%)	3,244 (21.8%)	-0.24
...MCR = MEDICARE; n (%)	22,409 (87.2%)	11,625 (78.2%)	0.24	-	-	-	-	-	#VALUE!	22,409 (87.2%)	11,625 (78.2%)	0.24
...MCD = MEDICAID; n (%)	0 (0.0%)	0 (0.0%)	#DIV/0!	-	-	-	-	-	#VALUE!	0 (0.0%)	0 (0.0%)	#DIV/0!
...NONE = NO BUSINESS LINE CODE (added in 2015); n (%)	0 (0.0%)	0 (0.0%)	#DIV/0!	-	-	-	-	-	#VALUE!	0 (0.0%)	0 (0.0%)	#DIV/0!
...UNK = UNKNOWN (added in 2015); n (%)	0 (0.0%)	0 (0.0%)	#DIV/0!	-	-	-	-	-	#VALUE!	0 (0.0%)	0 (0.0%)	#DIV/0!
Commercial vs Medicare Advantage- Data Type												
...1 - Fee For Service; n (%)	-	-	-	3,872 (12.0%)	4,189 (23.6%)	-0.31	-	-	-	3,872 (12.0%)	4,189 (23.6%)	-0.31
...2 - Encounter; n (%)	-	-	-	546 (1.7%)	502 (2.8%)	-0.07	-	-	-	546 (1.7%)	502 (2.8%)	-0.07
...3 - Medicare; n (%)	-	-	-	25,005 (77.4%)	12,039 (67.8%)	0.22	-	-	-	25,005 (77.4%)	12,039 (67.8%)	0.22
...4 - Medicare Encounter; n (%)	-	-	-	2,872 (8.9%)	1,018 (5.7%)	0.12	-	-	-	2,872 (8.9%)	1,018 (5.7%)	0.12

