Appendix B: Rivaroxaban vs Warfarin

Use of ACE inhibitors; n (%)	3,302 (36.9%)	3,351 (37.4%)	-0.01	4,037 (35.7%)	4,053 (35.9%)	0.00	12,056 (38.8%)	12,104 (39.0%)	0.00	19395 (37.8%)	19508 (38.0%)	0.00
Use of ARBs; n (%)	2,148 (24.0%)	2,097 (23.4%)	0.01	2,946 (26.1%)	2,929 (25.9%)	0.00	7,885 (25.4%)	7,901 (25.4%)	0.00	12979 (25.3%)	12927 (25.2%)	0.00
Use of Loop diuretics - United; n (%)	2,452 (27.4%)	2,457 (27.5%)	0.00	3,074 (27.2%)	2,962 (26.2%)	0.02	12,075 (38.9%)	12,145 (39.1%)	0.00	17601 (34.3%)	17564 (34.2%)	0.00
Use of other diuretics-United; n (%)	499 (5.6%)	452 (5.1%)	0.02	678 (6.0%)	628 (5.6%)	0.02	2,204 (7.1%)	2,206 (7.1%)	0.00	3381 (6.6%)	3286 (6.4%)	0.01
Use of nitrates-United; n (%)	721 (8.1%)	639 (7.1%)	0.04	1,067 (9.4%)	937 (8.3%)	0.04	3,909 (12.6%)	3,522 (11.3%)	0.04	5697 (11.1%)	5098 (9.9%)	0.04
Use of other hypertension drugs; n (%)	658 (7.4%)	690 (7.7%)	-0.01	798 (7.1%)	953 (8.4%)	-0.05	2,616 (8.4%)	2,741 (8.8%)	-0.01	4072 (7.9%)	4384 (8.5%)	-0.02
Use of digoxin- United; n (%)	1,060 (11.8%)	907 (10.1%)	0.05	1,932 (17.1%)	1,413 (12.5%)	0.13	4,898 (15.8%)	4,232 (13.6%)	0.06	7890 (15.4%)	6552 (12.8%)	0.07
Use of Anti-arrhythmics; n (%)	1,039 (11.6%)	1,022 (11.4%)	0.01	1,549 (13.7%)	1,578 (14.0%)	-0.01	3,969 (12.8%)	4,042 (13.0%)	-0.01	6557 (12.8%)	6642 (12.9%)	0.00
Use of COPD/asthma meds-United; n (%)	1,652 (18.5%)	1,660 (18.5%)	0.00	2,257 (20.0%)	2,211 (19.6%)	0.01	7,164 (23.1%)	6,884 (22.2%)	0.02	11073 (21.6%)	10755 (21.0%)	0.01
Use of statins; n (%)	5,403 (60.4%)	5,381 (60.1%)	0.01	6,725 (59.5%)	6,779 (60.0%)	-0.01	18,970 (61.1%)	19,049 (61.3%)	0.00	31098 (60.6%)	31209 (60.8%)	0.00
Use of other lipid-lowering drugs; n (%)	561 (6.3%)	570 (6.4%)	0.00	1,042 (9.2%)	1,077 (9.5%)	-0.01	2,197 (7.1%)	2,209 (7.1%)	0.00	3800 (7.4%)	3856 (7.5%)	0.00
Use of antiplatelet agents; n (%)	1,266 (14.1%)	1,275 (14.2%)	0.00	1,925 (17.0%)	1,862 (16.5%)	0.01	5,449 (17.5%)	5,400 (17.4%)	0.00	8640 (16.8%)	8537 (16.6%)	0.01
Use of heparin and other low-molecular weight heparins; n (%)	28 (0.3%)	48 (0.5%)	-0.03	1 (0.0%)	2 (0.0%)	#DIV/0!	191 (0.6%)	270 (0.9%)	-0.03	220 (0.4%)	320 (0.6%)	-0.03
Use of NSAIDs; n (%)	1,022 (11.4%)	1,003 (11.2%)	0.01	1,228 (10.9%)	1,245 (11.0%)	0.00	3,906 (12.6%)	3,909 (12.6%)	0.00	6156 (12.0%)	6157 (12.0%)	0.00
Use of oral corticosteroids; n (%)	1,770 (19.8%)	1,758 (19.6%)	0.01	2,198 (19.5%)	2,216 (19.6%)	0.00	7,748 (24.9%)	7,700 (24.8%)	0.00	11716 (22.8%)	11674 (22.7%)	0.00

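### Heparin/LMWH use is almost unrecorded in MarketScan (15 of 50,043 patients, against 2.6% in Optum and 4.2% in Medicare), so the MarketScan propensity score does not directly control it

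*Combined protocol and SAP*

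**What the plan says.** Section 9 calls for a 1:1 matched analysis whose propensity score holds the whole covariate list, leaving out only laboratory values. Appendix B is that list.

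- **Heparin/LMWH, unmatched** ("Use of heparin and other low-molecular weight heparins; n"). Optum then MarketScan, each as warfarin, rivaroxaban, standardized difference: "1,027 (4.0%) 48 (0.3%) 0.26 13 (0.0%) 2 (0.0%) #DIV/0". Medicare: "5,378 (5.8%) 271 (0.7%) 0.29". Pooled: "6418 (4.3%) 321 (0.4%) 0.26".
- **Heparin/LMWH, matched.** Optum then MarketScan: "28 (0.3%) 48 (0.5%) -0.03 1 (0.0%) 2 (0.0%) #DIV/0". Medicare has 191 and 270 of 31,068 per arm.
- **Comparison row** ("Use of fondaparinux or Bivalirudin; n"), unmatched, warfarin/rivaroxaban: 13/1 in Optum, 14/3 in MarketScan, 43/11 in Medicare.
- **Prasugrel** ("Use of Prasugrel; n"), unmatched: 43/58 in Optum, 69/88 in MarketScan, and suppressed in both Medicare arms, which means fewer than 11 in each. Appendix A uses the drug in exclusion 3d: "Aspirin (any dose) + thienopyridines (clopidogrel or prasugrel or ticlopidine".

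The document prints no code list for heparin or prasugrel and does not comment on the near-empty cells.

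**The concern.** Among warfarin starters, 4.0% in Optum and 5.8% in Medicare have recorded heparin use; in MarketScan it is 0.04%. A hundredfold drop in one commercial database, with other drug rows unchanged, looks like failed measurement rather than different practice.

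In Optum and Medicare, matching discards nearly all warfarin patients with recorded heparin (1,027 down to 28, and 5,378 down to 191). MarketScan cannot do this directly, so its matched warfarin arm may keep patients of a kind removed elsewhere, and the three estimates are then combined as if adjusted alike. The balance table does not reveal this. The MarketScan cell prints #DIV/0!, and the pooled matched row (220 and 320 of 51,318 per arm) counts almost all of the 11,300 MarketScan patients per arm as unexposed.

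**Working it through.** **1. Reproducing the printed standardized differences.** With p1 and p2 the printed rounded proportions, SMD = (p1 − p2) / √{[p1(1 − p1) + p2(1 − p2)] / 2}.

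- Optum: (0.040 − 0.003) / √{(0.0384 + 0.0030)/2} = 0.257; printed 0.26.
- Medicare: (0.058 − 0.007) / √{(0.0546 + 0.0070)/2} = 0.291; printed 0.29.
- Pooled: (0.043 − 0.004) / √{(0.0412 + 0.0040)/2} = 0.260; printed 0.26.
- MarketScan: both arms round to 0.0%, so the denominator is zero. That explains #DIV/0!.

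**2. Prevalence by database** (unmatched counts, both arms, Appendix B).

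| | Optum | MarketScan | Medicare |
|---|---|---|---|
| Patients | 25,701 + 14,869 = 40,570 | 32,295 + 17,748 = 50,043 | 92,403 + 40,652 = 133,055 |
| Heparin/LMWH | 1,075 (2.65%) | 15 (0.03%) | 5,649 (4.25%) |
| Fondaparinux/bivalirudin | 14 | 17 | 54 |
| Ratio of the two | 77 : 1 | 0.9 : 1 | 105 : 1 |

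The Section 5.3 flowchart ends at 50,085 for MarketScan; the difference of 42 does not matter here.

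**3. Do other drug rows agree?** Among warfarin starters, in the order Optum, MarketScan, Medicare:

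- fondaparinux/bivalirudin 0.051%, 0.043%, 0.047%
- statins 59.1%, 59.6%, 60.7%
- NSAIDs 8.6%, 8.3%, 9.1%
- bisphosphonates 4.0%, 4.1%, 3.9%

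**4. Expected MarketScan count.** At Optum's arm-specific rates: 32,295 × 1,027/25,701 + 17,748 × 48/14,869 = 1,290 + 57 ≈ 1,348. At Medicare's: 1,880 + 118 ≈ 1,998. Found: 15.

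**5. Strength as a predictor of treatment.** Odds ratio of recorded heparin use, warfarin against rivaroxaban: Optum (1,027/24,674) / (48/14,821) = 12.9; Medicare (5,378/87,025) / (271/40,381) = 9.2.

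**6. Size of a possible bias.** This is an assumption, because the documents give no outcome risk for heparin users. Suppose the unmatched imbalance of another database persisted in full in matched MarketScan, and heparin users had R times the outcome risk. The hazard ratio is then multiplied by [1 + p1(R − 1)] / [1 + p0(R − 1)], with p0 for warfarin and p1 for rivaroxaban.

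- Optum rates (p0 = 0.04, p1 = 0.0032): R = 1.5 gives 1.0016/1.0200 = 0.982; R = 3 gives 1.0064/1.0800 = 0.932.
- Medicare rates (p0 = 0.058, p1 = 0.0067): R = 1.5 gives 1.00335/1.0290 = 0.975; R = 3 gives 1.0134/1.1160 = 0.908.

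MarketScan supplies 165.658 of the 1,034.57 pooled expected events in Section 10, a weight of 0.160. The pooled multiplier runs from 0.982^0.160 = 0.997 to 0.908^0.160 = 0.985.

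**7. Prasugrel.** Optum 101/40,570 = 0.25%; MarketScan 157/50,043 = 0.31%; Medicare at most 20/133,055 = 0.015%. Expected in Medicare: about 313 at Optum rates and 399 at MarketScan rates. If only patients under 75 used it, at Optum rates, 0.00167 × 19,791 + 0.00390 × 10,708 ≈ 75. Ticagrelor in Medicare is 351/133,055 = 0.26%.

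**The case against.** **The cause is not shown.** A reader might infer that the MarketScan code list is wrong. The documents do not print it, and the fondaparinux comparison rests on small counts. A fault in the claims source or the platform attribute would look the same. This stands: the evidence supports failed capture, not a particular reason for it.

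**Heparin may be largely controlled through correlates.** In MarketScan, INR tests go from 1.90 against 0.23 (standardized difference 0.69) to 0.28 against 0.26 (0.02). PT/aPTT tests go from 0.64 to 0.02, and hospitalization in the prior 30 days from −0.18 to 0.00. Exclusion 3c also removes DVT and PE, another reason for heparin. It would therefore be too strong to say the imbalance is uncontrolled; it is not directly controlled. The residual after matching cannot be estimated from the documents, and the 0.26 to 0.29 is an unmatched figure from the other databases.

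**Predicting treatment is not confounding.** The documents do not link heparin to stroke or embolism. The baseline window in Section 6.2 includes the index date, so heparin dispensed together with warfarin may partly be a feature of starting warfarin. This limits any claim of bias. It does not remove the inconsistency: the plan treats heparin as a covariate, and that works in only two of the three databases.

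**Prasugrel has little consequence.** Suppression is policy, not an error, and gives only an upper bound; Medicare patients are also older. Where visible, the standardized difference is only −0.04 to −0.05, and clopidogrel and antiplatelet agents are matched in Medicare at 0.00. A reader might infer that exclusion 3d fails there. That depends on 3d using the same definition, which the documents do not say. It also needs concurrent aspirin, recorded in 418 + 266 = 684 of 133,055 (0.51%). Assuming independence, 75 to 399 prasugrel users would give roughly 0.4 to 2 affected patients.

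**Conclusion.** The concern holds as a measurement failure in one covariate in one database. MarketScan records 15 heparin/LMWH users where about 1,350 to 2,000 would be expected at the other databases' rates, so its propensity score does not meet the Section 9 specification for this covariate. The matched 1 against 2 describes a nearly empty flag and says nothing about balance in actual use.

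The consequence falls mainly on the MarketScan estimate: a multiplier of 0.98 to 0.91 if the whole unmatched imbalance persisted and heparin users had 1.5 to 3 times the risk. Under those assumptions the shift favours rivaroxaban, the same direction as the trial's 0.79, and could make MarketScan appear to agree with the trial. A reader might go further and infer that the pooled result is materially biased. The figures do not support that: even without help from the matched correlates, the pooled multiplier is only about 0.997 to 0.985. The repair is still worth making, because it is specific and, with Section 13 still blank, can be done without sight of outcomes. Prasugrel in Medicare is a secondary anomaly to verify.

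**What to change.** Before Section 13 is run:

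1. Trace why the MarketScan heparin/LMWH row is nearly empty (code list, claims source or platform attribute), repair it, and record the cause.
2. Tabulate the prevalence of every drug covariate across the three databases and explain any row that departs sharply. Include prasugrel in Medicare, and confirm which definition exclusion 3d uses.
3. Refit the MarketScan propensity score, re-match, and re-report the balance table and matched numbers, with standardized differences computed from unrounded proportions so that rare covariates do not print #DIV/0!.
4. If capture cannot be repaired, state that heparin/LMWH is unmeasured in MarketScan, show its pooled balance for Optum and Medicare only, and list it as a limitation of the MarketScan estimate.

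The cost is a definition check, one re-run in MarketScan (plus a small Medicare check), and possibly some lost MarketScan matches, which would slightly reduce its 166 expected events.
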